## **3. Outcome Measures**

Primary Outcome Measures: Lead (Pb), Cadmium (Cd), Gadolinium (Gd), Arsenic (As), Mercury (Hg), Cobalt (Co), Vanadium (V), Titanium (Ti), Sulfur (S), Chromium (Cr), Silver (Ag), Molybdenum (Mo), Boron (B), Lithium (Li), and Nickel (Ni) concentrations

## **4. Endpoints of the study:**

The primary outcome in these analyses will compare Lead (Pb), Cadmium (Cd), Gadolinium (Gd), Arsenic (As), Mercury (Hg), Cobalt (Co), Vanadium (V), Titanium (Ti), Sulfur (S), Chromium (Cr), Silver (Ag), Molybdenum (Mo), Boron (B), Lithium (Li), and Nickel (Ni) levels in the idiopathic POI group and control group.

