### 1. Participant Flow

#### Recruitment Details

This will be an observational prospective cohort study conducted at Obstetrics and Gynecology Department of Cengiz Gokcek Obstetrics and Children's Hospital between January 2020 and June 2021. The authors will be recruited 50 subjects with idiopathic POI, and 50 healthy patients were selected for the control group. All patients will be given their oral and written informed consent before their inclusion in the study. The protocol was approved by the Ethics Committee for Clinical Research of Gaziantep University (Reference number: 2020/362). The study strictly will be adhered to the principles of the Declaration of Helsinki.

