## **2. Baseline Characteristics**

In order for the expectation that a medium effect size ( $d = 0.60$ ) would occur between the physiological parameters of the POI group and the control group was statistically significant, the required minimum number in each group was determined as 45 ( $\alpha=0,05$ ;  $1-\beta=0,80$ ). It was decided to include the same number of participants of control groups to balance the POI and control groups. Power analysis was performed by using G power package version 3.9.1. Kolmogorov Smirnov and Shapiro Wilk tests will be used to test the normal distribution of data. For comparing groups (POI/control) the student t-test will be used for variables that have a normal distribution, and the Mann Whitney U test will be used for variables that have not a normal distribution. The ROC analysis will be applied for the determination of cut-off point for variables. Moreover, Spearman correlation test will be used for the relationship of between variables. SPSS for Windows 22.0 and Medcalc programs will be used for statistical analysis.  $p<0.05$  will be accepted as statistical significance.

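### Fifteen primary element comparisons are each tested at p<0.05 with no multiplicity control: if no element differs, the chance of at least one false positive is 54% under independence and still 14% at an assumed correlation of 0.9.

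*Combined protocol and SAP*

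**What the plan says.** Section 3 of the combined protocol and SAP (Outcome Measures) lists 15 concentrations as primary: "Primary Outcome Measures: Lead (Pb), Cadmium (Cd), Gadolinium (Gd), Arsenic (As), Mercury (Hg), Cobalt (Co), Vanadium (V), Titanium (Ti"), followed by S, Cr, Ag, Mo, B, Li and Ni. Section 4 (Endpoints) repeats the same 15 as the primary comparison between the two groups: "The primary outcome in these analyses will compare Lead (Pb), Cadmium (Cd), Gadolinium (Gd), Arsenic (As), Mercury (Hg") and the remaining ten. None is ranked or singled out.

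The statistical methods are in section 2 (Baseline Characteristics). Normally distributed variables are compared by Student's t-test; otherwise "the Mann Whitney U test will be used for variables that have not a normal distribution". One threshold is given: p<0.05 "will be accepted as statistical significance". The sample size is one calculation with d = 0.60, alpha 0.05 and power 0.80, from which "the required minimum number in each group was determined as 45". Recruitment Details in section 1 plans "50 subjects with idiopathic POI, and 50 healthy patients were selected for the control group".

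The document does not mention a multiplicity adjustment, a hierarchy, a global test or an exploratory status for any of the 15 comparisons.

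**The concern.** When 15 outcomes are all primary and each has its own 5% test, the 5% describes each test and not the set. As written, any element with p<0.05 counts as a significant primary finding, so the study has 15 chances to produce one by luck. The plan gives a reader no way to tell such a finding from a real difference. It also does not commit to reporting all 15 p-values, so readers may be unable to make the correction themselves.

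The sample size has the same gap. Its alpha and power describe one comparison, while the primary outcome consists of 15.

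**Working it through.** **Inputs from the document.** Primary comparisons: k = 15 (sections 3 and 4). Threshold per test: 0.05 (section 2). Design values: d = 0.60, alpha 0.05, power 0.80, minimum 45 per group (section 2). Planned size: 50 per group (section 1). Sidedness is not stated.

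**Assumptions.** Tests are two-sided. The document gives no correlation between elements, so a common correlation ρ is varied.

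**1. The plan's own sample size.** For a two-sample t-test with n per group, the degrees of freedom are 2n − 2 and the noncentrality is d·√(n/2).
- n = 44: 0.60 × √22 = 2.81, power 79.5%.
- n = 45: 0.60 × √22.5 = 2.85, power 80.4%.

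The solution is n = 44.59, rounded up to 45, so the stated figure reproduces for **one** two-sided test at 0.05. A one-sided test would need only about 35 to 36.

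**2. Family-wise error with no true differences.** With independent elements it is 1 − (1 − 0.05)^15 = 1 − 0.463 = **53.7%**. For equally correlated, normally distributed test statistics, let c = 1.96 and integrate over a shared standard normal factor u:

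FWER = 1 − ∫ φ(u) · [Φ((c − √ρ·u)/√(1−ρ)) − Φ((−c − √ρ·u)/√(1−ρ))]^15 du

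| Assumed ρ | Chance of at least one false positive |
|---|---|
| 0 | 53.7% |
| 0.3 | 45.7% |
| 0.5 | 36.1% |
| 0.7 | 25.6% |
| 0.9 | 14.4% |
| 0.95 | 11.0% |

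A simulation of actual t-tests with 50 per group at ρ = 0.9 gave 14.2%, in agreement.

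**3. Power per element if the 15 tests are controlled.** The Bonferroni level is 0.05/15 = 0.0033. It holds family-wise error at 1 − (1 − 0.0033)^15 = 4.9% under independence. t-test power at d = 0.60:

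| n per group | alpha 0.05 | alpha 0.05/15 |
|---|---|---|
| 45 | 80.4% | 43.7% |
| 50 | 84.4% | 50.0% |

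At 0.05/15, 80% power at d = 0.60 needs 82 per group (81 gives 79.7%, 82 gives 80.4%). With 50 per group, 80% power is reached at about d = 0.77. On normal data, simulated Mann-Whitney power is slightly lower: 78% and 82% at 0.05, and 40% and 46% at 0.05/15, for 45 and 50 per group.

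**4. An illustrative mixed case.** Suppose 3 of the 15 elements truly differ at d = 0.60, the elements are independent, and there are 50 per group. This scenario is assumed and does not come from the document. Results from 200,000 simulated studies:

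| | Unadjusted | Benjamini-Hochberg | Holm |
|---|---|---|---|
| At least one false element | 46% | 11% | 4% |
| Share of all declared elements that are false | 19% | 6.5% | 2.8% |
| Average power for the true elements | 84% | 61% | 51% |

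The unadjusted 46% agrees with 1 − 0.95^12 for the 12 null elements. At ρ = 0.5 (20,000 studies) the first row becomes 32%, 8% and 3%.

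**The case against.** The study is observational, tests no treatment, and does not define success as any one element being significant. The endpoints can be read as 15 separate questions, each with its own 5% error, and family-wise control in element-by-element screening is partly a matter of choice. Accepting a false discovery rate approach concedes as much. The 54% figure assumes independence, the least favourable case shown, although all elements are measured in the same women. Section 2 never claims joint power across the 15, and its per-parameter calculation is correct. Adjustment also has a real cost in power.

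Part of this stands. A screening aim would be legitimate, family-wise control is not the only defensible target, and the single-comparison calculation contains no error. But the document calls all 15 elements primary and never describes the study as screening or exploratory. Correlation reduces the excess without removing it: even at 0.95 the rate is about twice the nominal 5%. The loss of power is the consequence of having 15 primary outcomes; the present plan does not show it. A rule chosen after the p-values are known would not be pre-specified.

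**Conclusion.** The concern holds. Followed as written, the primary analysis has a family-wise error above 5% at every correlation examined when no element differs: 53.7% under independence, falling to 14.4% at ρ = 0.9 and 11.0% at ρ = 0.95. The count of 15, the single threshold and the absence of any control come directly from the document. The common correlations and two-sided testing are assumptions.

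The stated alpha and power are valid for one of the 15 tests only. The planned 50 per group does not give 80% power at d = 0.60 for each element at the Bonferroni level. The planned ROC and Spearman analyses are not counted in these figures. Because this is the primary analysis and the correction is cheap, it should be corrected before the data are analysed.

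**What to change.** In section 2:

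1. State that Holm's procedure will be applied across the 15 primary elements to hold family-wise error at 5%. If the study is meant as a screen, say so and name Benjamini-Hochberg with a 5% false discovery rate as the target, noting that this does not hold family-wise error at 5% once some elements truly differ.
2. Commit to reporting raw and adjusted p-values for all 15 elements.
3. Label p-values from the ROC and Spearman analyses exploratory.
4. Restate the power sentence as t-test values for one element at d = 0.60: at two-sided 0.05, 80% with 45 per group and 84% with 50; at 0.0033, a conservative benchmark for Holm, about 44% and 50%. Add that 50 per group gives 80% power at about d = 0.77 at that level, and that Mann-Whitney power will differ.

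**Cost.** New wording and one calculation on p-values the study will have anyway; no extra participants, samples or assays. The price is sensitivity: in the illustrative case, average power falls from 84% to 61% with Benjamini-Hochberg or 51% with Holm. The power statement also becomes less favourable. Keeping 80% power at d = 0.60 at the Bonferroni level would take 82 per group, so without enlarging the study the text should state the lower power.

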## **5. Limitations and strengths:**

There will strengths of this study. The women participating in the study had idiopathic POI and had not received treatment.

## **6. Certain Agreements**

The authors declare that they have no conflict of interest.

